#### Abstract

##### Objectives:

##### Primary Objectives

##### Phase II:

The primary objective of the Phase II portion of the trial is to define the overall response rate, defined as the combination of complete (CR) and partial (PR) response rates, of TAK228 in patients with relapsed lymphoma.

##### Secondary Objectives

##### Phase II:

The secondary objectives of the Phase II portion of the trial are to define the safety & tolerability, progression free survival, duration of response, and overall survival of TAK228 in patients with relapsed lymphoma.

##### Exploratory Objectives

The exploratory objectives are to define:

- Determination of response associated clinical characteristics,
- The incidence of activating mutations in MTOR and related genes in patients who respond to TAK228 in their archival lymphoma biopsy tissue,
- The change in phosphorylation of mTORC1/2 target proteins and related signaling proteins at baseline and after therapy with TAK228 in peripheral blood mononuclear cells by utilizing reverse phase protein array,
- The change in phosphorylation of mTORC1/2 target proteins and related signaling proteins at baseline and after therapy with TAK228 in optional pre- and post- therapy biopsy by utilizing reverse phase protein array

##### Rationale: (Be as concise as possible)

The mTOR pathway is an active target in multiple lymphoma subtypes. mTOR activity has been shown to be increased in nearly all lymphoma subtypes, including diffuse large B cell, mantle cell, and Hodgkin

lymphomas. The rapalog mTOR inhibitors (Temsirolimus and Everolimus) directly effect mTORC1 and have demonstrated promising efficacy in multiple lymphoma subtypes.

Temsirolimus is approved in Europe for mantle cell lymphoma, and has shown promising responses in diffuse large b-cell, follicular, and other indolent lymphomas. Everolimus has also shown promising responses in relapsed aggressive lymphoma. In addition, Everolimus has shown impressive response in relapsed/refractory Hodgkin lymphoma.

It is now known that inhibition of mTORC1, although effective for a portion of patients with lymphoma, leads to transient benefit at best, and perhaps even tumor growth for some cancers. Demonstrating the complexity of the crosstalk found in this pathway, mTORC1 inhibition can lead to activation of the PI3K pathway due to mTORC2 negative feedback, resulting in phosphorylation of Akt.

We believe inhibition of both mTORC1 and mTORC2 with TAK228 may result in a significant improvement in the efficacy seen to date with mTORC1 inhibitors in lymphomas. This clinical trial is based on: 1) the known promising activity of mTORC1 inhibitors in various subtypes of lymphomas, 2) the known escape/resistance mechanism that cancer utilizes to overcome mTORC1 inhibitor via mTORC2 stimulation of Akt, and 3) the early signal of excellent tolerance and efficacy of TAK228 in clinical trials thus far.

It is our hypothesis that TAK228 will result in response rates higher than previously seen with rapalogs, with acceptable tolerability. The goal of our trial is to identify lymphoma subtypes with high response rates for future clinical trials, either combined with current standard therapies or with novel targeted agents.

It is currently difficult to predict which patients will have response to mTOR pathway directed therapies due to lack of actionable biomarkers. It is possible to assess for the activity of mTOR inhibition by evaluation of phosphorylation of downstream targets of mTOR, such as S6K and 4EBP1. To evaluate the baseline phosphorylation and effect of TAK228 on these markers, we propose to collect peripheral blood mononuclear cells and archival tissue blocks from patients enrolled on trial for correlative studies. The peripheral blood mononuclear cells will be evaluated as a surrogate for mTORC1/2 inhibition and Akt phosphorylation after exposure to TAK228 via reverse phase protein array (RPPA). For the list of the 217 currently utilized antibodies in the MD Anderson RPPA platform. Archival tumor blocks will be stored for attempted correlation of clinical responders vs non-responders with genomic assessment.

It has recently been reported that mutations of the MTOR may activate the pathway and thus predict clinical response to mTOR inhibitors. Patients with available archival tissue will undergo an evaluation for the presence of an MTOR mutation which could serve as a potential biomarker in future clinical trials.

### **Eligibility: (List All Criteria)**

#### **Inclusion:**

- 1) Each patient must meet all of the following inclusion criteria to be enrolled in the study: 1. Male or female patients 18 years or older.
- 2) Voluntary written consent must be given before performance of any study related procedure not part of standard medical care, with the understanding that consent may be withdrawn by the patient at any time without prejudice to future medical care.
- 3) Female patients who: are postmenopausal for at least 1 year before the screening visit, OR are surgically sterile, OR if they are of childbearing potential, agree to practice 1 effective methods of contraception and one additional effective (barrier) method, at the same time, from the time of signing the informed consent through 90 days (or longer, as mandated by local labeling [eg, USPI, SmPC, etc;]) after the last dose of study drug, or agree to practice true abstinence, when this is in line with the preferred and usual lifestyle of the patient (Periodic abstinence [e.g, calendar, ovulation, symptothermal, postovulation

methods] and withdrawal, spermicides only, and lactational amenorrhea are not acceptable methods of contraception. Female and male condoms should not be used together.

4) Male patients, even if surgically sterilized (ie, status post-vasectomy), who: agree to practice highly effective barrier contraception during the entire study treatment period and through 120 days after the last dose of study drug, or agree to practice true abstinence, when this is in line with the preferred and usual lifestyle of the patient (Periodic abstinence [e.g, calendar, ovulation, symptothermal, postovulation methods for the female partner] and withdrawal, spermicides only, and lactational amenorrhea are not acceptable methods of contraception. Female and male condoms should not be used together; Agree not to donate sperm during the course of this study or 120 days after receiving their last dose of study drug

5) Patients must have a diagnosis of prior treated diffuse large b-cell lymphoma, mantle cell lymphoma, transformed lymphoma, follicular lymphoma (any grade), small lymphocytic lymphoma, marginal zone lymphoma, or Hodgkin lymphoma with at least 2 lines of therapy without a curative treatment options.

6) Eastern Cooperative Oncology Group (ECOG) performance status and/or other performance status  $\leq 2$ .

7) Adequate organ function, as specified below, within 3 weeks before the first dose of study drug: a) Bone marrow reserve consistent with: absolute neutrophil count (ANC)  $\geq 1.5 \times 10^9/L$ ; platelet count  $\geq 100 \times 10^9/L$ ; hemoglobin  $\geq 9$  g/dL without transfusion within 1 week preceding study drug administration; b) Hepatic: total bilirubin  $\leq 1.5 \times$  upper limit of normal (ULN), transaminases (aspartate aminotransferase-AST and alanine aminotransferase ALT)  $\leq 2.5 \times$  ULN ( $\leq 5 \times$  ULN if liver metastases are present); c) Renal: creatinine clearance  $\geq 50$  mL/min based either on Cockcroft-Gault estimate or based on urine collection (12 or 24 hour); d) Metabolic: fasting serum glucose ( $\leq 130$  mg/dL) and fasting triglycerides  $\leq 300$  mg/dL;

8) Ability to swallow oral medications;

9) Measurable disease, defined as  $\geq 1.5$  cm on imaging assessment.

#### **Exclusion:**

1) Eligible for therapy for the lymphoid malignancy which has a high likelihood of a curative result in the opinion of the investigator.

2) Female patients who are both lactating and breastfeeding or have a positive serum pregnancy test during the screening period

3) Any serious medical or psychiatric illness that could, in the investigator's opinion, potentially interfere with the completion of treatment according to this protocol

4) Concurrent malignancies except basal or squamous cell carcinoma of the skin, or cervical carcinoma in situ treated with curative intent. Any cancer from which the patient has been disease free for at least 2 years is permissible.

5) Treatment with any investigational products within 14 days before the first dose of study drug

6) Failed to recover to baseline or stable grade 1 from the reversible effects of prior anticancer therapies with the exception of alopecia.

7) Manifestations of malabsorption due to prior gastrointestinal (GI) surgery, GI disease, or for an unknown reason that may alter the absorption of TAK228; such as significant chronic diarrhea. In addition, patients with enteric stomata are also excluded.

- 8) Poorly controlled diabetes mellitus defined as HbA1c > 7%; subjects with a history of transient glucose intolerance due to corticosteroid administration are allowed in this study if all other inclusion/exclusion criteria are met;
- 9) History of any of the following within the last 6 months prior to study entry: ischemic myocardial event, including angina requiring therapy and artery revascularization procedures; Ischemic cerebrovascular event, including TIA and artery revascularization procedures; Requirement for inotropic support (excluding digoxin) or serious (uncontrolled) cardiac arrhythmia (including atrial flutter/fibrillation, ventricular fibrillation or ventricular tachycardia); Placement of a pacemaker for control of rhythm; New York Heart Association (NYHA) Class III or IV heart failure; Pulmonary embolism.
- 10) History of any of the following within the last 6 months prior to study entry: Requirement of inotropic support; Serious uncontrolled cardiac arrhythmia (including atrial flutter/fibrillation, ventricular fibrillation or ventricular tachycardia); Placement of a pacemaker for control of rhythm
- 11) Significant active cardiovascular or pulmonary disease at the time of study entry, including: uncontrolled high blood pressure (i.e., systolic blood pressure >180 mm Hg, diastolic blood pressure > 95 mm Hg) Use of anti-hypertensive agents to control hypertension before cycle 1 day 1 is allowed; Pulmonary hypertension; Uncontrolled asthma or O2 saturation < 90% by ABG (Arterial Blood Gas) analysis or pulse oximetry on room air; Significant valvular disease; severe regurgitation or stenosis by imaging independent of symptom control with medical intervention, or history of valve replacement; medically significant (symptomatic) bradycardia; History of arrhythmia requiring an implantable cardiac defibrillator; Baseline prolongation of the rate-corrected QT interval (QTc) (e.g., repeated demonstration of QTc interval > 480 milliseconds, or history of congenital long QT syndrome, or torsades de pointes).
- 12) Treatment with strong inhibitors and/or inducers of cytochrome P450 (CYP) 3A4, CYP2C9 or CYP2C19 within 1 week preceding the first dose of study drug.
- 13) Patients receiving systemic corticosteroids (either IV or oral steroids, excluding inhalers or low-dose hormone replacement therapy as defined no greater than 20mg of prednisone daily) within 1 week before administration of the first dose of study drug.
- 14) Other clinically significant co-morbidities, such as uncontrolled pulmonary disease, active central nervous system disease, active infection, or any other condition that could compromise participation of the patient in the study.
- 15) Central nervous system (CNS) lymphoma.
- 16) Known human immunodeficiency virus infection.
- 17) Known hepatitis B surface antigen-positive, or known or suspected active hepatitis C infection.
- 18) Diagnosed or treated for another malignancy within 2 years before administration of the first dose of study drug, or previously diagnosed with another malignancy and have any evidence of residual disease. Patients with nonmelanoma skin cancer or carcinoma in situ of any type are not excluded if they have undergone complete resection
- 19) Daily or chronic use of a proton pump inhibitor (PPI) and/or having taken a PPI within 7 days before receiving the first dose of study drug

**Are patients <18 years of age eligible to participate in this study?**  Yes  No

**Studies that include children must meet the criteria for inclusion.**

[http://www.fda.gov/ohrms/dockets/AC/04/briefing/4028B1\\_05\\_NIH-Inclusion%20of%20Children.doc](http://www.fda.gov/ohrms/dockets/AC/04/briefing/4028B1_05_NIH-Inclusion%20of%20Children.doc)  
<http://www.hhs.gov/ohrp/policy/populations/children.html>

**Studies that exclude children must have appropriate justification. Please select all that apply:**

Phase I or Phase II study targeting cancer that is very unusual in pediatrics (e.g., prostate, lung, breast, chronic lymphocytic leukemia, etc.)

Are participants >65 years of age eligible to participate in this study?  Yes  No

Are pregnant women eligible to participate in this study?  Yes  No

Will the recruitment population at M. D. Anderson include persons who are incarcerated at time of enrollment (e.g., prisoners) or likely to become incarcerated during the study?

Yes  No

**Disease Group:**

Lymphoma

**Treatment Agents/Devices/Interventions:**

TAK228

**Proposed Treatment/Study Plan:**

Is treatment assignment randomized?  Yes  No

Is this a blinded or double-blinded study?  Yes  No

TAK228 milled API will be administered once daily at approximately the same time on each scheduled dosing day and not to take more than the prescribed dose at any time. It is recommended that each dose of TAK228 be given orally with 8 ounces (240 mL) of water. TAK228 should be administered on an empty stomach, and patients should be instructed to refrain from eating or drinking (aside from water and prescribed medications) for 2 hours before and 1 hour after each dose. Cycles are repeated every 28 days.

### **Screening Evaluation**

A history and physical examination, including performance status evaluation, height, weight, and vital signs, should be performed within 28 days prior to the first dose of TAK228.

The following laboratory studies should be performed within 3 days prior to the first dose of TAK228 – CBC with differential, Serum chemistries – sodium (Na), potassium (K), chloride (Cl), glucose, bicarbonate (CO2), blood urea nitrogen (BUN), creatinine (Cr), calcium (Ca), magnesium (Mg), phosphorus, total protein, albumin, alkaline phosphatase, aspartate transaminase (AST), alanine transaminase (ALT), total bilirubin, direct bilirubin, uric acid, lactate dehydrogenase (LDH), Beta-2 microglobulin, prothrombin time (PT/INR), partial thromboplastin time (PTT), hemoglobin A1c, and urine analysis, and a fasting serum glucose, triglycerides, cholesterol panel, and serum Beta-HCG in women of child-bearing potential. Fasting is defined as nothing to eat for at least 4-6 hours before blood draw.

ECHO or MUGA performed.

Quantitative immunoglobulins (IgG, IgA, and IgM) within 28 days prior to the first dose of TAK228.

HIV 1 and 2 antibody, Hepatitis C viral antibody, Hepatitis B surface antigen, Hepatitis B core antibody within 28 days prior to the first dose of TAK228.

The following staging studies should be performed within 28 days prior to the first dose of TAK228 – CT scans of neck, chest, abdomen, and pelvis; Chest X-ray – PA and lateral; and unilateral bone marrow biopsy and unilateral bone marrow aspirate. An optional PET/CT scan may be obtained within 28 days prior to the first dose of TAK228 at the discretion of the treating physician.

An electrocardiogram will be obtained within 28 days prior to the first dose of TAK228.

For correlative studies, an optional 10 ml of blood sample [2 heparin containing green top tubes (5 ml/tube)] will be collected within 3 business days prior to the first dose of TAK228. These samples will be transported within 4 hours of collection to the RPPA Core Laboratory Facility and/or Lymphoma Tissue Bank, depending on time of collection, at M. D. Anderson Cancer Center (MDACC). Blood from green top tubes will be processed for isolation of peripheral blood mononuclear cells (PBMC) using standard laboratory protocols.

For correlative studies, an optional archival tumor FFPE biopsy material collection will be occur for analysis of mutations in MTOR.

For correlative studies, an optional biopsy will be collected within 28 days prior to the first dose of TAK228 for analysis of phosphorylation in mTOR and related proteins if the patient has a tumor deemed to be safely accessible by the treating physician.

#### **EVALUATION DURING STUDY**

During the first cycle, patients will be evaluated by the treating physician in the clinic prior to the start of TAK228 (within 3 business days). A relevant history and physical examination, including performance status evaluation and vital signs, will be recorded within 3 business days of the first dose of TAK228. Patients will subsequently be assessed by the medical team on days 8, 15, and 22 (within 3 business days). At these weekly assessments, a relevant history and physical examination will be recorded. Toxicities will be graded according to the NCI CTC v4.0 during these visits.

For all cycles beyond cycle 1, patients will be evaluated by the treating physician in the clinic prior to each cycle of TAK228 (within 3 business days). A relevant history and physical examination, including performance status evaluation and vital signs, will be recorded within 3 business days of each dose of TAK228. Toxicities will be graded according to the NCI CTC v4.0 during these visits

The following laboratory studies should be performed within 3 business days prior to each cycle of TAK228 – CBC with differential, Serum chemistries - Na, K, Cl, CO2, BUN, Cr, Ca, Mg, phosphorus, total protein, albumin, alkaline phosphatase, AST, ALT, total bilirubin, direct bilirubin, urinalysis, uric acid, PT/PTT/INR and LDH, and a fasting serum glucose, triglycerides, cholesterol panel, and serum Beta-HCG in women of child-bearing potential.

During the first 2 cycles of therapy, patients will monitor their glucose at least once daily in a fasting state via a provided glucometer. All patients will self monitor their glucose daily in a fasting state approximately the same time each day, and if directed by the clinical trial team may require monitoring more than once per day. If no irregularities in the fasting blood glucose level are observed during a minimum of 2 consecutive months, then the frequency of in-home fasting blood glucose testing can be reduced to a minimum frequency of once weekly, depending on the investigator's judgement and approval. Fasting is defined as nothing to eat for at least 4-6 hours before blood draw.

During the first cycle of TAK228, the following laboratory studies should be performed on day 15 (within 3 business days) - CBC with differential, Serum chemistries - Na, K, Cl, CO2, BUN, Cr, Ca, Mg, phosphorus, total protein, albumin, alkaline phosphatase, AST, ALT, total bilirubin, uric acid, and LDH, and a fasting serum glucose, triglycerides, cholesterol panel. Fasting is defined as nothing to eat for at

least 4-6 hours before blood draw.

Hemoglobin A1c should be obtained prior to cycle 1 day 1, cycle 3 day 1, cycle 6 day 1, cycle 9 days 1 and cycle 12 day 1.

An electrocardiogram will be obtained pre-dose (within 28 business days) prior to start of cycle 1 and within 3 days of starting each subsequent cycle.

The following staging studies should be performed at completion of 2 cycles of TAK228 (within 5 business days prior to starting cycle 3) – CT scans of neck, chest, abdomen, and pelvis; Chest X-ray – PA and lateral; and unilateral bone marrow biopsy and unilateral aspirate if bone marrow is involved with lymphoma at baseline. An optional PET/CT scan may be obtained at completion of 2 cycles of TAK228 at the discretion of the treating physician.

The following staging studies should be performed at completion of every 2 cycles beyond the first 2 cycles of TAK228 (i.e., +/- 5 business days prior to starting cycle 5, 7, 9, and 11): CT scans of neck, chest, abdomen, and pelvis; Chest X-ray – PA and lateral; and optional unilateral bone marrow biopsy and unilateral aspirate if bone marrow is involved with lymphoma at baseline at the discretion of the treating physician; An optional PET/CT scan may be obtained at completion of every 2 cycles of TAK228 at the discretion of the treating physician, but should be considered if previously FDG avid lymph nodes remain enlarged on CT imaging or physical examination.

In consenting patients, for correlative studies, a 10 ml of blood sample [1 heparin containing green top tube and 1 purple top tube (5 ml/tube)] will be collected at each of the following time points: cycle 1 day 1 (2-4 hours after dose), and cycle 2 day 1 (2-4 hours after dose). These samples will be transported within 4 hours (+/- 2 hours) of collection to the RPPA Core Laboratory Facility and/or Lymphoma Tissue Bank, depending on time of collection, at M. D. Anderson Cancer Center (MDACC). Blood from green top tubes will be processed for isolation of peripheral blood mononuclear cells (PBMC) using standard laboratory protocols.

For correlative studies, an optional biopsy will be collected on day 14 (+/- 5 business days, within 4 hours of dosing) for analysis of phosphorylation of mTORC1/2 target proteins if the patient has a tumor deemed to be safely accessible by the treating physician and underwent Screening Biopsy.

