#### **Evaluation At Completion of Study**

Patients will be evaluated by the treating physician and a relevant history and physical examination, including performance status evaluation and vital signs, will be recorded 1 week (+/- 7 business days) after completion of TAK228. Toxicities will be graded according to the NCI CTC v4.0 during this visit.

The following laboratory studies should be performed 1 week (+/- 7 business days) after completion of TAK228 – CBC with differential, Serum chemistries - Na, K, Cl, Glucose, CO2, BUN, Cr, Ca, Mg, phosphorus, total protein, albumin, alkaline phosphatase, AST, ALT, total bilirubin, PT/PTT/INR, urinalysis, uric acid, LDH, and quantitative immunoglobulins, and a fasting serum glucose, triglycerides, and cholesterol panel. In addition, an EKG should be performed 1 week (+/- 7 business days) after completion of TAK228. Fasting is defined as nothing to eat for at least 4-6 hours before blood draw.

The following staging studies should be performed 2 weeks (+/- 14 business days) after completion of TAK228 – CT scans of neck, chest, abdomen, and pelvis; Chest X-ray – PA and lateral; and optional bilateral bone marrow biopsy and unilateral aspirate if bone marrow is involved with lymphoma at baseline at the discretion of the treating physician. An optional PET/CT may be performed 2 weeks (+/- 14 working/business days) after completion of TAK228 at the discretion of the treating physician.

For correlative studies, 10 ml of blood sample [2 heparin containing green top tubes (5ml/tube)] will be collected when a patient is taken off study (+/- 14 business days). These samples will be transported within 6 hours of collection to the RPPA Core Laboratory Facility and/or Lymphoma Tissue Bank, depending on time of collection, at M. D. Anderson Cancer Center (MDACC). Blood from green top tubes will be processed for isolation of peripheral blood mononuclear cells (PBMC) using standard laboratory protocols.

Patients will be evaluated by the treating physician and a relevant history and physical examination, including performance status evaluation and vital signs, will be recorded 1 week (+/- 7 business days) after completion of TAK228. Toxicities will be graded according to the NCI CTC v4.0 during this visit.

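### The transport limit for the mononuclear-cell blood is 4 hours at baseline but up to 6 hours at every later visit, so longer transport could be mixed with the drug effect in the exploratory phosphoprotein analysis

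*Combined protocol and SAP*

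**What the plan says.** The Exploratory Objectives include measuring "The change in phosphorylation of mTORC1/2 target proteins and related signaling proteins at baseline and after therapy with TAK228 in peripheral blood mononuclear cells", with RPPA as the assay. Three sections set the rules for drawing and moving the blood.

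- **Screening Evaluation (baseline).** The draw, which precedes the start of treatment, is described as "an optional 10 ml of blood sample [2 heparin containing green top tubes (5 ml/tube)] will be collected within 3 business days prior". On transport: "These samples will be transported within 4 hours of collection to the RPPA Core Laboratory Facility".
- **Evaluation During Study (cycle 1 day 1 and cycle 2 day 1, each 2-4 hours after dosing).** The 10 ml is made up of "1 heparin containing green top tube and 1 purple top tube", at 5 ml per tube. On transport: "These samples will be transported within 4 hours (+/- 2 hours) of collection".
- **Evaluation At Completion of Study (off study; the paragraph appears twice).** Two 5 ml green-top tubes are drawn. On transport: "These samples will be transported within 6 hours of collection to the RPPA Core Laboratory Facility".

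Screening Evaluation says "Blood from green top tubes will be processed for isolation of peripheral blood mononuclear cells (PBMC) using standard laboratory protocols", and the other two sections say the same. No use is stated for the purple-top tube. The Analysis Plan and Efficacy Analysis sections give no method for the RPPA change from baseline. Nothing in the documents requires the time from collection to processing to be recorded.

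**The concern.** The analysis compares each patient's later samples with that patient's own baseline. The trial is not randomized and has no untreated group, so anything that changes systematically between baseline and later visits enters the estimated change together with the drug. Here the plan itself sets a looser transport limit on the post-baseline side of every pair. An allowance that was equally loose at all visits would mainly add noise. One that is loose only after baseline can add bias.

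What is at stake is how the pharmacodynamic result is read. The Rationale uses PBMC as a surrogate for mTORC1/2 inhibition and Akt phosphorylation after exposure to TAK228. If a shift appears, a reader should be able to rule out sample handling as its source. Without recorded times, the documents give no means of checking this afterwards.

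**Working it through.** The plan states no figure for this comparison (no effect size, variance or test), so there is nothing to reproduce. The check sets the three collection paragraphs side by side.

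| | Baseline | On treatment (C1D1, C2D1) | Off study |
|---|---|---|---|
| Source section | Screening Evaluation | Evaluation During Study | Evaluation At Completion of Study |
| Tubes (5 ml each) | 2 green | 1 green + 1 purple | 2 green |
| Total blood | 2 × 5 = 10 ml | 1 × 5 + 1 × 5 = 10 ml | 2 × 5 = 10 ml |
| Green-top blood for PBMC | 2 × 5 = 10 ml | 1 × 5 = 5 ml | 2 × 5 = 10 ml |
| Longest permitted transport | 4 h | 4 + 2 = 6 h | 6 h |
| Tube type used for PBMC | heparin green | heparin green | heparin green |

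**Transport.** The ceiling after baseline exceeds the baseline ceiling by 6 − 4 = 2 hours, and 2 / 4 = 50%. The difference always runs the same way: no post-baseline visit has a limit as tight as baseline. A two-sided tolerance on an upper limit is also unclear. It could mean a limit of 6 hours, or a window from 4 − 2 = 2 to 4 + 2 = 6 hours. The ceiling is 6 hours on either reading.

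**Volume.** Green-top blood on treatment is 5 / 10 = half the baseline amount. This may affect cell yield. Nothing in the documents links volume to the phosphorylation signal.

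**Tube type.** PBMC are taken from green-top tubes at all visits, so the purple tube does not change the assayed material as the plan is written.

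**Could actual times differ by visit?** Baseline blood may be drawn at any time in the 3 business days before the first dose, while on-treatment blood is tied to 2-4 hours after a dose. All three sections send samples to the RPPA core laboratory and/or the tissue bank according to the time of collection. Time of day, and with it the destination, can therefore differ between baseline and treatment. This is an inference from the text, not evidence of delay.

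**What cannot be computed.** The documents contain no data on how the phosphoprotein signal changes with time to processing, so neither the sign nor the size of any bias follows from them.

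**The case against.** The strongest reply is that the limits are permitted maxima, not observed times. Every sample could arrive well within 4 hours, and up to 4 hours the permitted ranges overlap. The study runs at one centre, the destinations are the same two in-house facilities at each visit, and nothing shows that on-treatment blood will take longer. This stands. A reader might infer that the change from baseline is confounded; the documents support only that it could be, if the extra allowance is used.

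A reader might also infer two further things that the documents do not support:

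- *That the purple tube brings a different anticoagulant into the assay.* Each section takes PBMC from green-top tubes. Only green-top volume differs.
- *That longer transport would imitate mTORC1/2 inhibition.* This needs the signal to fall with delay, and the documents contain no stability data.

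It can also be said that a handling effect would not be wholly inseparable from the drug. Off-study samples share the 6-hour ceiling with on-treatment samples, so comparing those two holds the ceiling constant. The panel has 217 antibodies, so a general handling effect could be looked for outside the mTOR pathway. Both checks are possible but imperfect: disease state, time since last dose and green-top volume differ between on-treatment and off-study draws, and the plan specifies neither check.

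Finally, the objective is exploratory, the sampling is optional, and processing follows standard laboratory protocols that are not among the documents. This limits the weight of the point but does not remove it.

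**Conclusion.** The point holds as a minor, cheaply corrected weakness. The permitted transport time is 4 hours at baseline and up to 6 hours on treatment and off study, and green-top volume is 10, 5 and 10 ml respectively. Because the RPPA analysis is an uncontrolled within-patient change, any effect of longer transport could be mixed with the drug effect.

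This conclusion rests on two assumptions that the documents neither confirm nor exclude: that some post-baseline samples use the extra 2 hours, and that the assay is sensitive to that delay. If either fails, transport time introduces no bias. The size and direction of any bias are unknown.

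The reach is confined to the exploratory PBMC objective. The response endpoint and the Bayesian stopping boundaries do not use these samples.

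**What to change.** 1. Amend the blood-collection paragraphs in Screening Evaluation, Evaluation During Study and both copies in Evaluation At Completion of Study to one common transport limit, for example the baseline 4 hours, stated as a plain maximum without the two-sided tolerance.
2. Record the time from collection to processing for every sample. Matching transport limits alone does not match processing delay, because no visit has a limit from arrival to processing.
3. State in the Analysis Plan that the change-from-baseline analysis will be repeated without pairs in which either sample falls outside the common limit.
4. State what the purple-top tube is for. If it is not needed, draw the same green-top volume at every visit. If it is needed, keep it and say why.

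**Cost.** These rules stand in the protocol text, so the change is a protocol amendment. A tighter limit may lose a few late samples. Replacing the purple tube with a second green one keeps the draw at 10 ml. Keeping it alongside two green tubes makes 3 × 5 = 15 ml, an extra 5 ml per on-treatment draw. If the sponsor prefers to leave the limits as they are, recording the times would still allow the question to be examined.
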